## **2 STUDY GOAL AND OBJECTIVES**

Patients with NDD-CKD, who have evidence of systemic inflammation with increased cardiovascular risk, will be enrolled into this trial. The purpose of this trial is to determine a dose to select for a potential cardiovascular outcome trial with Ziltivekimab. The current trial will determine which dose of Ziltivekimab will have a significant reduction in hs-CRP with acceptable increases in LDL-C or triglycerides and without clinically meaningful reductions in neutrophils and platelet counts. Doses to be tested will be 7.5 mg, 15 mg and 30 mg subcutaneous monthly compared to placebo for six months.

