**Table 2 SCHEDULE OF PROCEDURES**

	Screening 										Treatment Period					Safety F/U 	
	-2	-1	1	2	3	4	5	6	N/A	7	8	9	10	11/ET	12	13/ET	
Visit Number	-2	-1	1	2	3	4	5	6	N/A	7	8	9	10	11/ET	12	13/ET	
Visit Day Window	-14	-7	1	8	22	29-35	43-49	57-63	78-84	85-91	113-119	141-147	155-161	162-168	190-196	218-224	
Visit Window		±2		±2													
Visit Week	-2	-1	1	2	4	5	7	9		13	17	21	23	24/ET	28	32/ET	
Lipid Profile by NMR spectroscopy (fasting 8 hours) 			X							X			X		X		
Cardiac Risk Biomarker 			X							X			X		X		
Storage samples for Exploratory Biomarkers and RNA Testing 			X							X			X		X		
DNA Testing (Stored Blood Samples)			X							X			X		X		
Limited Physical Examination 		X													X		
INR 		X	X	X	X	X	X	X		X	X	X	X		X		
Adverse Events		X	X	X	X	X	X	X		X	X	X	X		X		
PROMIS® 13a and Fatigue Items 			X							X			X		X		
PROMIS® Sexual Interest Items 			X							X			X		X		
CARES (Corvidia ePRO) 		X			X					X			X		X		
PGIS 		X			X					X			X		X		
PGIC 					X					X			X		X		
Optum SF-36 v2® 			X		X					X			X		X		
EQ-5D-5L 			X		X					X			X		X		

ET = Early Termination; F/U = Follow-up.

1. If a Screening laboratory (excluding hematology) result is outside inclusion criteria parameters screening may be extended up to one week to allow for retesting of lab test(s) that did not meet inclusion criteria.
2. Vital signs include temperature, respiratory rate, heart rate, and blood pressure (patients may be re-evaluated within 2 weeks, at the discretion of the PI if anti-hypertensive therapy has been started or increased as a result of initial screening blood pressure). Whenever possible, vital signs will be obtained after at least 5 minutes resting in the supine position or, when necessary, in a semi-recumbent position. Vital signs will be done prior to ECG recordings.
3. Hematology: hemoglobin, hematocrit, reticulocyte count, red blood count (RBC) indices (e.g., mean corpuscular volume (MCV), red cell distribution width (RDW), platelets, white blood count (WBC), WBC differential.
4. Lipids and subfractions (fasting 8 hours): total cholesterol, low density lipoprotein (LDL) cholesterol, high density lipoprotein (HDL), and triglycerides; Lp(a), ApoB, ApoA1.

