5. Chemistry: sodium, potassium, chloride, bicarbonate (or CO2), calcium, phosphate, alanine aminotransferase (AST), blood urea nitrogen (BUN) creatinine, total bilirubin, direct bilirubin, alkaline phosphatase, albumin, glucose and eGFR calculated by CKD-EPI Creatinine Equation (<https://www.kidney.org/content/ckd-epi-creatinine-equation-2009>).
6. At Weeks 1 and 24, a portion of urine will be stored frozen for future analysis.
7. Iron Indices: TSAT, ferritin, iron, total iron binding capacity (TIBC).
8. Infectious Disease Screen: HIV 1 and 2, Hepatitis B surface antigen, Hepatitis C antibody, mycobacterium tuberculosis test (e.g., QuantiferON) is preferred, but a purified protein derivative (PPD) skin test read within 48-72 hours by a qualified healthcare professional can be performed. If the test comes back unable to perform analysis or indeterminate or confirmatory testing is required, the screening window is extended until central laboratory results are available. (<https://www.cdc.gov/tb/publications/factsheets/testing/skintesting.htm>).
9. Special RBC: reticulocyte hemoglobin content (CHr).
10. IL-6: Interleukin-6. Pre-dose sampling.
11. hs-CRP: high-sensitivity C-reactive protein. Test can be repeated once prior to randomization visit. Results after screening will be blinded after the first dose.
12. Pregnancy: β-hCG; FSH: Follicle Stimulating Hormone.
13. On dosing Weeks 1, 5, 9, 13, 17, and 21, trough PK samples to be collected within approximately -0.5 h pre-dose. Single PK blood samples will also be collected on Weeks 2, 4, 7, 23, 24/ET, 28, and 32/ET around the same time as the pre-dose samples were collected on previous dosing visits.
14. On dosing weeks 1, 5, 9, 13, 17, and 21, ADA: Anti-drug antibodies specimens to be collected within approximately 0.5 h pre-dose.
15. Standard 12-lead ECG will be recorded in the supine position (or with the patient as flat as possible) after vital signs assessments. The ECG will be locally read by the Investigator.
16. Chronic Kidney Disease (CKD) Biomarkers: cystatin C and UACR.
17. Cardiac Risk marker: SSA, fibrinogen and ST2.
18. Exploratory storage samples will be two 5-ml tubes of plasma, two 5-ml tubes of serum, and two 5-mL tubes of whole blood (PBMC testing at Screening, Week 13 and Week 24).

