### **5.2                   Screening Visit Procedures (Week -1; Days -7 to -1) – Full Screening**

Every effort should be made to obtain the blood tests for each visit on the same day of the week (e.g. on Wednesdays).

The following list summarizes the procedures for Week -1. Please see [Table 2](#) for full details.

- Medical History
- Concomitant and Prior Medications
- Vital Signs
- Hematology
- Lipids (fasting 8 hours)
- Chemistry

- Spot urine protein-creatinine ratio
- Infectious Disease Screen (If the test comes back unable to perform analysis or indeterminate or confirmatory testing is required, the screening window is extended until central laboratory results are available)
- Serum Pregnancy, FSH
- 12-lead ECG
- CKD Biomarkers
- NT-pro-BNP
- Lp(a), ApoB, ApoA1 (fasting 8 hours)
- Storage samples for Exploratory Biomarkers and RNA Testing (PBMC testing)
- DNA Testing – Stored Blood Samples
- Limited Physical Examination
- CARES Corvidia ePRO
- PGIS

The following sections summarize the procedures for the Treatment Period. Please see [Table 2](#) for full details.

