### **11.3.3 Analysis Windows and Baseline**

If data are collected by visit, the data will be analyzed by visit based on the protocol-planned visits. If multiple records are collected for a visit, the latest record will be used for the summary for that visit.

The observational period for the study will start from informed consent and end with study completion (see [Section 4.4](#) for the definition of study completion). Any event occurring after the defined observational period, even if collected on the CRF, may not be included in the planned statistical analysis. However, all data, including that reported after the defined observational period, will be included in the patient data listings.

For evaluations that are collected at multiple occasions prior to initiation of Study Drug, the latest evaluation will be considered the "Baseline" evaluation for analysis, unless otherwise specified.

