#### 11.4.4.3 Exploratory

- Difference in percent change in hs-CRP levels from Baseline to End of Treatment (Weeks 23 through 24) between each active group and placebo.
- Difference in percent change in serum NT-pro-BNP from Baseline (average of the NT-pro-BNP value prior to randomization and Day 1) to Week 13 and to End of Treatment (Weeks 23 through 24) between each active group and placebo.
- Difference in change in SAA from Baseline to End of Treatment (Weeks 23 through 24) between each active group and placebo.
- Difference in percent change in fibrinogen from Baseline to End of Treatment (Week 24) between each active group and placebo.
- Difference in change in hemoglobin from Baseline (average of the two most recent hemoglobin values prior to randomization and Day 1) to Week 13 and to End of Treatment (Weeks 23 through 24) between each active group and placebo.
- Difference in change in serum albumin from Baseline (average of the two most recent serum albumin values prior to randomization and Day 1) to Week 13 and to End of Treatment (Weeks 23 through 24) between each active group and placebo.
- Proportion of patients achieving hs-CRP response at Week 13 and to End of Treatment (Weeks 23 through 24), defined as hs-CRP <2.0 mg/L in each active group and placebo.
- Difference in change in ST2 from Baseline to Week 13 and to End of Treatment (Week 24) between each active group and placebo.
- Difference in percent change in Lp(a) from Baseline to Week 13 and to End of Treatment (Weeks 23 through 24) between each active group and placebo.

- Difference in percent change in LDL-C, triglycerides, ApoB, ApoA1, ApoB/ApoA1, and lipid profile by NMR spectroscopy from Baseline to Week 13 and to End of Treatment (Weeks 23 through 24) between each active group and placebo.
- Difference in change of creatinine based eGFR and cystatin C-based eGFR from Baseline to Week 13 and to the End of Treatment (Weeks 23 through 24) between each active group and placebo.
- Difference in change of UACR from Baseline to Week 13 and to End of Treatment (Weeks 23 through 24) between each active group and placebo.
- Difference in change of the total fatigue score (PROMIS Fatigue 13a short form and selected items from the PROMIS Fatigue item bank) from Baseline to Week 13 and to End of Treatment (Weeks 23 through 24) between each active group and placebo.

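### Section 11.3.3 keeps only the Day 1 value as lipid baseline; averaging it with the fasting Week -1 value already drawn would tighten the LDL-C and triglyceride comparisons at no sampling cost

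*Protocol*

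**What the plan says.** **Default rule.** Section 11.3.3 states: "For evaluations that are collected at multiple occasions prior to initiation of Study Drug, the latest evaluation will be considered the" Baseline evaluation, subject to any specific rule elsewhere.

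**Exceptions.** The endpoint lists (Sections 11.4.4.1 and 11.4.4.3) give an averaged baseline for four variables only: hs-CRP, NT-pro-BNP, hemoglobin and albumin. The hemoglobin rule, for example, is the "average of the two most recent hemoglobin values prior to randomization and Day 1".

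**Lipid endpoint.** Section 11.4.4.3 lists "Difference in percent change in LDL-C, triglycerides, ApoB, ApoA1, ApoB/ApoA1, and lipid profile by NMR spectroscopy from Baseline to Week 13" and End of Treatment, each active group against placebo, without a baseline definition of its own. Lp(a) is treated the same way in a separate item.

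**What is drawn before the first dose.** Section 5.2 (Week -1) has an entry beginning "Lipids (fasting 8 hours" and also lists Lp(a), ApoB and ApoA1 (fasting), NT-pro-BNP and the CKD biomarkers. Section 5.3.1 (Day 1, pre-dose) lists all of these again. Hematology and chemistry are drawn three times: at initial screening (Section 5.1), at Week -1 and on Day 1.

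**Role of the markers.** Section 2 says the dose is to be chosen on a significant hs-CRP reduction with "acceptable increases in LDL-C or triglycerides and without clinically meaningful reductions in neutrophils and platelet counts".

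**The concern.** For LDL-C, triglycerides, Lp(a), ApoB and ApoA1 the trial pays for two fasting pre-dose readings and analyses one. A single reading carries visit-to-visit noise into the baseline covariate of the mixed model and, because lipids are analysed as percent change, into the denominator as well. The interval for each active-placebo difference is then wider than the collected data require.

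The protocol gives no reason for treating lipids differently from NT-pro-BNP, which is drawn at the same two visits and averaged. LDL-C and triglycerides also bear on the dose decision, while the sample size in Section 11.1 rests on hs-CRP alone, so no precision is stated for them. Precision that costs nothing is worth having there.

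**Working it through.** **1. The plan's own figure.** Section 11.1 gives a difference of 60.74 percentage points, SD 16.893, 54 per group and two-sided alpha 0.05.
- Standard error: 16.893 × √(2/54) = 3.25.
- 60.74 / 3.25 = 18.7, so power is essentially 1, in line with the stated figure above 99%.
- Dropout: 54 / 0.9 = 60 per group.

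Both reproduce. This calculation concerns hs-CRP, whose baseline is already averaged, so the point below does not touch it.

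**2. Number of planned pre-dose readings (from the visit lists in Sections 5.1, 5.2 and 5.3.1).**

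| Variable | Readings | Baseline used | Entry limit |
|---|---|---|---|
| NT-pro-BNP | 2 | average | no |
| LDL-C, triglycerides, Lp(a), ApoB, ApoA1 | 2 | Day 1 | no |
| Cystatin C, UACR | 2 | Day 1 | none on the marker itself |
| Neutrophils, platelets | 3 | Day 1 | yes |
| Creatinine eGFR | 3 | Day 1 | yes |
| SAA, fibrinogen | 1 | Day 1 | no |

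The panel contents come from the footnotes to Table 2: hematology includes "platelets, white blood count (WBC), WBC differential", chemistry includes "eGFR calculated by CKD-EPI Creatinine Equation", and the CKD panel is "Chronic Kidney Disease (CKD) Biomarkers: cystatin C and UACR".

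**3. Gain for the baseline-adjusted comparison with two readings.** Assume that any two visits correlate equally at r. The residual variance, in units of the total variance, is:
- one baseline: 1 − r² = (1−r)(1+r);
- mean of two: 1 − 2r²/(1+r) = (1−r)(1+2r)/(1+r).

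The ratio is (1+2r)/(1+r)².

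| r (assumed) | variance ratio | fall in SE | 54 per group is worth |
|---|---|---|---|
| 0.5 | 2.0/2.25 = 0.89 | 5.7% | 61 |
| 0.7 | 2.4/2.89 = 0.83 | 8.9% | 65 |
| 0.9 | 2.8/3.61 = 0.78 | 11.9% | 70 |

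A simulation on the percent-change scale (log-normal marker; between-patient CV 0.3 or 0.5, within-patient CV 0.10 to 0.30, all assumed; r about 0.7 to 0.9) gave reductions in the adjusted SE of 11.9% to 15.1%.

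**4. When the equal-correlation assumption fails.** Let the two baseline readings correlate at 0.8 and Day 1 with Week 13 at 0.7. Let Week -1 correlate with Week 13 at p. With Day 1 alone the residual variance is 1 − 0.49 = 0.51. With the mean it is 1 − ((0.7+p)/2)²/0.9.

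| p (assumed) | residual variance | change in SE |
|---|---|---|
| 0.70 | 0.456 | −5.5% |
| 0.65 | 0.494 | −1.6% |
| 0.60 | 0.531 | +2.0% |

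In this example break-even is where ((0.7+p)/2)² = 0.9 × 0.49 = 0.441, that is p ≈ 0.63.

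**5. Neutrophils and platelets.** Section 11.4.5.2 provides only descriptive changes from baseline. Under equal correlation the variance of an unadjusted change is proportional to (1−r)(1 + 1/k), where k is the number of baseline readings. Moving from k = 1 to k = 3 takes 2 to 1.33, a fall of one third in variance and 18.4% in SE. That figure rests on the same assumption and takes no account of the entry limits.

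**The case against.** The last pre-dose value is an ordinary convention. Section 11.3.3 leaves room for exceptions, and the protocol sends analysis detail to an SAP that is not shown. Nothing is misstated or biased. All of this stands and is why the point is offered as an improvement, not as an error. What remains is that this document fixes the default and departs from it for a marker drawn at the same visits as the lipids.

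A reader might infer more than the documents support:
- **That all the affected markers decide the dose.** Section 2 names LDL-C, triglycerides, neutrophils and platelets beside hs-CRP. It does not name eGFR or UACR, which are exploratory and analysed as change, so they have no baseline denominator.
- **That a tested conclusion is weakened.** The primary endpoint already uses an average. SAA and fibrinogen have a single pre-dose draw. The lipid endpoints are exploratory and were never sized, so the patient equivalents above only express precision.
- **That every screening value should be averaged for every laboratory variable.** Neutrophils, platelets (Section 4.2, exclusions 1 and 2) and eGFR (Section 4.1, criterion 2) are screened against limits. Averaging in those values adds regression to the mean to within-group changes, which is what Section 11.4.5.2 summarises for the two cell counts. The effect is equal across arms in expectation. In addition, Table 2 footnote 1 allows retesting of failed screening tests other than hematology, so the number of values averaged would depend on the first result.

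Two further cautions stand. The key safety readouts for the two cell counts in Section 3.1.2 are absolute thresholds that do not involve baseline. And antihypertensive treatment may change during screening (Section 4.2, exclusion 14), so Day 1 may describe the pre-dose state of the kidney markers better.

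**Conclusion.** The point holds as a cheap gain in precision for the lipid variables. The default discards a scheduled fasting Week -1 value of LDL-C, triglycerides, Lp(a), ApoB and ApoA1, and two of these matter for dose choice. If visits are equally correlated with r between 0.5 and 0.9, using it lowers the standard error by about 6% to 12%. The documents give no r, and the gain disappears if Week -1 predicts Week 13 clearly less well than Day 1 does. With the two draws at most about a week apart and Week 13 some three months later, a large gap is possible but is not the natural expectation.

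There is no bias in the randomized comparison and no effect on the primary endpoint, the secondary endpoints or the stated power. The case for neutrophils, platelets and creatinine eGFR is weaker because of their entry limits, and does not justify replacing their Day 1 baseline in the main summaries.

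**What to change.** - **Lipids.** In Section 11.3.3, define Baseline for LDL-C, triglycerides, Lp(a), ApoB and ApoA1 (and hence their ratio) as the mean of the scheduled Week -1 and Day 1 pre-dose values. Use the geometric mean if the analysis is on the log scale, and the available value if one is missing.
- **Cystatin C and UACR.** The same definition may be used, as an option.
- **Neutrophils, platelets and creatinine eGFR.** Keep Day 1 for the main summaries. Add, if wanted, a supplementary between-arm comparison with a baseline averaged over scheduled draws only, excluding retests, and note the regression to the mean in within-group changes.
- **Variables with one pre-dose draw** (SAA, fibrinogen, ST2, hepcidin, CHr, NMR profile): no change.

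The cost is a sentence or two in Section 11.3.3, repeated in the SAP and fixed before unblinding for the Week 13 analysis. No new samples are needed. If screening is extended, the two lipid readings may lie further apart, which reduces the gain somewhat.

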### **11.3.4 Missing Data Handling**

Unless otherwise specified, missing data will not be imputed and the analyses will be based on observed data only.

## **11.4 Statistical Analyses**

### **11.4.1 Demographic and Background Characteristics**

Patient demographics and baseline characteristics will be summarized by treatment group using the ITT, per-protocol, and safety populations

### **11.4.2 Study Drug and Concomitant Medications**

Summaries of prior (pre-baseline) medications and concomitant (baseline or later) medications will be provided by treatment group using the safety population. Prior medications are defined as medications given before the first dose of study drug. Concomitant medications are defined as medications taken before and continuing after first

dose of study drug or initiated after first dose of study drug. Medications will be coded with World Health Organization (WHO) Drug Dictionary. Patients will be counted only once by medication class or name.

#### ***11.4.3 Efficacy Analysis***

For all efficacy variables, the number of patients (n), mean, standard deviation (SD), median, quartiles (Q1 and Q3), minimum (min) and maximum (max) values for the observed value, change from baseline, or percent change from baseline (as applicable) will be reported. The difference (Ziltivekimab - Placebo) in changes or percent changes (as applicable) will be presented.

A mixed model for repeated measures (MMRM) will be used to evaluate change or percent change from baseline. The model will include variables for baseline hemoglobin ( $\geq 11$  or  $< 11$  g/dL), CKD Stage (3, 4 or 5), treatment group, visit and treatment group-by-visit interaction as categorical fixed effects, baseline value and baseline-by-visit interaction will be included as covariates. The least squares means for each dose, the least squares mean differences from placebo along with the associated 95% confidence intervals (CIs) and p-values will be presented. If the normality assumption is not met, a nonparametric test will be selected for efficacy analysis. Details of normality test and nonparametric test will be provided in the Statistical Analysis Plan.

An unstructured covariance matrix will be used to model the within-subject correlation. The Kenward-Roger approximation will be used to adjust the denominator degrees of freedom. The analysis will be performed based on all observed post-baseline scores without any imputation of missing data. In the case when the MMRM fails to converge using an unstructured covariance matrix in any stage, a less stringent covariance matrix (e.g., autoregressive 1) will be used.

Sensitivity analyses will be conducted to explore the robustness of the result for primary efficacy endpoint based on MMRM. Full details will be pre-specified in SAP and documented prior to database lock of the study.

The differences in proportions and 95% CIs will be based on the normal approximation to binomials.

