#### **3.1.3.2 Secondary**

All secondary and exploratory analyses will be performed with the Intent-to-Treat (ITT) population.

- Difference in change in SAA from Baseline to Week 13 between each active group and placebo.
- Difference in percent change in fibrinogen from Baseline to Week 13 between each active group and placebo.

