## 4 SELECTION OF STUDY POPULATION AND CRITERIA FOR WITHDRAWAL

### 4.1 Inclusion Criteria

After signing an informed consent form approved by the Investigator's Institutional Review Board (IRB) or Independent Ethics Committee (IEC) to be eligible, potential study patients must meet all of the following criteria:

- 1) Age  $\geq 18$  years at the time of signing of the Informed Consent Form (ICF).
- 2) Stage 3-5 NDD-CKD, i.e. estimated glomerular filtration rate (eGFR)  $>10$  and  $<60$  mL/min/1.73 m^2 using the CKD-EPI Creatinine Equation ([www.kidney.org/content/ckd-epi-creatinine-equation-2009](http://www.kidney.org/content/ckd-epi-creatinine-equation-2009)).
- 3) Serum hs-CRP level  $\geq 2.0$  mg/L measured during the Screening Period. (Note: C-reactive protein may not be commonly measured in patients with CKD. Targeting patients with a history of advanced stage CKD, ASCVD, anemia, metabolic syndrome, diabetic retinopathy and diabetes for screening will help increase the chances of identifying patients with CRP  $\geq 2.0$ )
- 4) The patient agrees to comply with the contraception and reproduction restrictions of the study ([Appendix G](#)):
  - a) Women of childbearing potential must be using a method of contraception, that is "highly effective" (i.e.,  $<1\%$  failure rate) for at least 3 months following the last dose of study drug;
  - b) Postmenopausal women must have had no menstrual bleeding for at least 1 year before initial dosing and either be over the age of 60-years or have an elevated plasma follicle-stimulating hormone (FSH) level (i.e.,  $>40$  mIU/mL) at Screening;
  - c) Women of childbearing potential must have a documented negative pregnancy test result at Screening. Patients with elevated  $\beta$ -HCG levels believed to be due to end-stage renal disease may be enrolled if documented to not be pregnant;

AND

All male patients, from the day of dosing until the final study visit, unless surgically sterile, must be willing to use a condom with a partner (male patients with partners of childbearing potential must be willing to use 2 effective methods of birth control, 1 should be condom with spermicide) to prevent pregnancy and drug exposure of a partner, and refrain from donating sperm or fathering a child.

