#### **4.3 Criteria for Discontinuation of Study Drug**

It may be necessary for a participant to permanently discontinue study intervention. If study intervention is permanently discontinued, the participant shall remain in the study to be evaluated on all early termination and safety follow-up procedures per the Schedule of Assessments (SOA) in [Section 5.3.9](#) and [Section 5.6](#). Study drug may be prematurely discontinued for a number of reasons, including:

- An intercurrent illness at the discretion of the investigator;
- Any intolerable AE that cannot be ameliorated by appropriate medical intervention or that in the opinion of the Medical Monitor or Investigator would lead to undue risk if the patient were to continue on treatment;
- In the event of severe injection related reactions, anaphylaxis, or hypersensitivity ([Section 8.2](#) and [Section 4.5](#));
- If at any point during the study,  $\geq 10\%$  of subjects enrolled experience anaphylaxis, additional enrollment will stop in the study, and all patients in the study will discontinue receiving study drug ([Section 8.2](#) and [Section 4.4](#));
- Pregnancy;
- Organ transplantation or development of another indication for chronic immunosuppression;

Reasons for all withdrawals/discontinuations of Study Drug will be recorded, and the Medical Monitor should be informed of all such cases as they occur. Temporary discontinuation of study intervention and restarts may be performed per [Section 4.5](#).

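### The all-observed-values rule would analyse eGFR measured after the start of maintenance dialysis or after a transplant as the patient's own kidney function (exploratory eGFR endpoints only)

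*Protocol*

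**What the plan says.** Section 11.4.3 of the protocol specifies an MMRM for change or percent change in the efficacy variables and states the data rule for it: "The analysis will be performed based on all observed post-baseline scores without any imputation of missing data". Section 11.3.4 gives the general rule, introduced by an unless-otherwise-specified clause: "missing data will not be imputed and the analyses will be based on observed data only". Section 3.1.3.2 sets the population: "All secondary and exploratory analyses will be performed with the Intent-to-Treat (ITT) population".

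The endpoints concerned are in section 11.4.4.3: "Difference in change of creatinine based eGFR and cystatin C-based eGFR from Baseline to Week 13 and to the End of Treatment". Section 2.5 presents cystatin C and estimated GFR as markers of kidney function.

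On who is enrolled and what happens to them:

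- Section 4.1 requires stage 3 to 5 CKD not on dialysis, with eGFR above 10 and below 60 mL/min/1.73 m².
- Section 4.2, exclusion 19, bars patients with a previous transplant and those expected to receive one during the study.
- Section 4.3 lists among the reasons for stopping study drug "Organ transplantation or development of another indication for chronic immunosuppression". The participant then stays in the study for early-termination and safety follow-up procedures.
- Section 5.6 makes the early-termination visit before Week 24 a repeat of the Week 24 procedures. Section 5.3.9 shows that these include chemistry and the CKD biomarkers.
- Starting dialysis is not mentioned in section 4.3 (stopping drug), 4.5 (temporary suspension) or 4.6 (withdrawal), nor as an endpoint.

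**The concern.** Being off dialysis is a condition of entry only. A patient who enters with an eGFR a little above 10 could start maintenance dialysis during the 24-week treatment period, and the protocol does not say what then happens to that patient's kidney measurements. After dialysis starts, the filtration marker in blood also reflects clearance by dialysis. After a transplant it reflects the graft. In neither case does the computed eGFR describe change in the patient's own kidneys, which is what the objective asks about.

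The error runs in the favourable direction, because the worst kidney outcome can be entered as little loss or a gain. If such events fell unevenly across arms, the eGFR comparison would be shifted towards the arm with more of them. The number of kidney failures that would explain the shift is not among the results the protocol asks for.

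**Working it through.** **1. The plan's own figures.** Section 11.1 gives no figure for eGFR. Its hs-CRP calculation (difference 60.74, SD 16.893, 54 per group, two-sided alpha 0.05) reproduces: power is 1.00 to rounding, consistent with the stated value above 99%. The dropout allowance also reproduces: 54 / 0.90 = 60 per group and 4 × 60 = 240. Nothing in this point changes those figures. The 54 serves below as the analysed number per arm.

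**2. Does the text admit the values?**

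- *After dialysis starts.* No rule removes the patient or the measurement, so unless drug or participation is stopped for another reason the visit schedule continues. Section 5.3.7 collects chemistry and CKD biomarkers at Week 13, and section 5.3.9 at Weeks 23 and 24. Table 2 notes 5 and 16 confirm that these supply creatinine-based eGFR and cystatin C. Each result is an observed post-baseline value in a randomised patient, and section 11.4.3 uses it.
- *After a transplant.* Study drug stops, but sections 4.3, 5.3.9 and 5.6 together yield one early-termination measurement of both markers, at a visit labelled Week 24/ET. The visits at Weeks 28 and 32 add chemistry but no CKD biomarkers (section 5.4). Section 11.3.3 analyses data by planned visit and does not say whether an early-termination value takes the Week 24 slot, so entry into the End of Treatment endpoint is possible but not certain.

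**3. Size, for illustration.** The protocol gives neither an expected number of events nor an SD for eGFR change. If k patients in an arm of 54 have a recorded eGFR that exceeds native function by g units, the simple arm mean moves by

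shift = k × g / 54.

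Assume three dialysis starts in one arm, each read 3 to 6 units too high:

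- 3 × 3 / 54 = 0.17 mL/min/1.73 m²
- 3 × 6 / 54 = 0.33 mL/min/1.73 m²

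For scale, assume an SD of change of 6. The 95% half-width for a difference between two arms is then 1.96 × 6 × √(2/54) = 2.26. The shifts are 0.17 / 2.26 = 7% and 0.33 / 2.26 = 15% of it. If the comparison arm has the same number of events with the same gap, the shift in the difference is zero.

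**The case against.** **This is SAP detail.** Section 11 refers details of all planned analyses to the SAP, which was not available here. The sentence on observed values is also a standard statement that missing data are not imputed, written for every efficacy variable. This has some force: an SAP could define which values are evaluable. But section 11.4.3 hands over specific items (normality testing, the nonparametric test and sensitivity analyses for the primary endpoint). It does not hand over the data rule, which it states without exception. The point therefore concerns text that is present.

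**Little depends on it.** This stands. Section 2 ties dose selection to hs-CRP, LDL-C or triglycerides, neutrophils and platelets. The eGFR endpoints are exploratory, and section 11.4.4.4 applies multiplicity control to the primary endpoint only.

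**Stronger readings a reader might infer.**

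- *That one event could be a third of the confidence-interval half-width.* One transplant with an assumed rise of 40 units gives 40 / 54 = 0.74, and 0.74 / 2.26 = 0.33. The documents do not support using this as the size. Exclusion 19 leaves only unforeseen transplants, and such a patient supplies mainly one early-termination value. The ratio also ignores the outlier's own variance: 36 + 40² × (1/54) × (53/54) is about 65, so the half-width is 1.96 × √((36 + 65)/54), about 2.7, and the ratio about 0.28. If the nonparametric fallback in section 11.4.3 applied, one extreme value would count for less.
- *That UACR is affected in the same way.* The value would no longer describe the same kidney state, but its direction after dialysis is uncertain and it may be missing if there is no urine. No favourable bias is shown.
- *That an arm with more kidney failures will look better.* This is possible under the stated rule. Nothing in the protocol indicates how many events there will be or that they will differ by arm.

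**Conclusion.** The point holds, at low importance, for the creatinine-based and cystatin C-based eGFR endpoints. As written, the protocol would treat values obtained after maintenance dialysis begins, and possibly an early-termination value after a transplant, as observed native kidney function. The size cannot be computed from the protocol. The dialysis illustration is a modest fraction of the assumed half-width, and its gap, event count and SD are all assumptions without a source in the document. Bias in a treatment comparison further requires uneven events between arms. The primary and secondary endpoints, the sample size and the testing sequence are not affected.

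**What to change.** Before unblinding for the Week 13 analysis, add to the analysis text for the two eGFR endpoints:

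1. Values measured after the start of maintenance dialysis or after a transplant are not used as observed kidney function.
2. The number of patients with such a start is reported by arm next to the eGFR results, so that setting values aside does not hide the events.
3. A sensitivity analysis counts the start as an unfavourable outcome, for example by assigning the worst rank. A fixed low eGFR is a more debatable choice, because it costs a patient who entered just above 10 very little and a stage 3 patient a great deal.
4. The start date of maintenance dialysis and of any transplant is confirmed to be captured. The protocol names no dedicated field, so its availability from adverse-event or other records should be checked rather than assumed.

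The cost is a short addition to the analysis text, a check of the data collection, a few values set aside and one extra sensitivity analysis. No dose, visit or treatment rule changes.
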